## 4.2 Exclusion Criteria

**4.2.1** HER2-positive breast cancer defined as IHC3+ or IHC2+ with FISH $\geq$ 2 AND copy number  $\geq$ 4 OR FISH  $\leq$ 2 AND copy number  $\geq$ 6

**4.2.2** Inflammatory breast cancer

**4.2.3** Contraindication(s) to breast-conserving therapy

**4.2.4** Contraindication to radiation therapy or planned partial breast irradiation

**4.2.5** Patients with cosmetic breast augmentations, specifically sub glandular implants with altered breast tissue, at the time of diagnosis

**4.2.6** Evidence of metastatic disease.

**4.2.7** Diagnosis of immunodeficiency or is receiving chronic systemic steroid therapy (in dosing exceeding 10 mg daily of prednisone equivalent) or any other form of immunosuppressive therapy within 7 days prior to the first dose of study drug.

**4.2.8** Known additional malignancy that is progressing or has required active treatment within the past 3 years. Note: Participants with basal cell carcinoma of the skin, squamous cell carcinoma of the skin, or carcinoma in situ (e.g. breast carcinoma, cervical cancer in situ) that have undergone potentially curative therapy are not excluded.

**4.2.9** Medical history and concurrent diseases

- Active autoimmune disease that has required systemic treatment in the past 2 years (i.e. with use of disease modifying agents, corticosteroids or immunosuppressive drugs). Replacement therapy (eg., thyroxine, insulin, or physiologic corticosteroid replacement therapy for adrenal or pituitary insufficiency, etc.) is not considered a form of systemic treatment.
- History of (non-infectious) pneumonitis that required steroids or has current pneumonitis.
- Active infection requiring systemic therapy.
- Any serious or uncontrolled medical disorder that, in the opinion of the investigator, may increase the risk associated with study participation or study drug administration, impair the ability of the subject to receive protocol therapy, or interfere with the interpretation of study results.
- Known history of Human Immunodeficiency Virus (HIV) (HIV 1/2 antibodies).
- Known history of Hepatitis B (e.g., HBsAg reactive) or known active Hepatitis C (e.g., HCV RNA [qualitative] is detected).

**4.2.10** Prohibited Treatments and/or Therapies

- Chronic use of immunosuppressants and/or systemic corticosteroids (used in the management of cancer or non-cancer-related illnesses). However, use of corticosteroids is allowed for the treatment of immune related Adverse Events (irAEs), or adrenal insufficiency.
- Live vaccines within 30 days prior to the first dose of study treatment and while participating in the study. Examples of live vaccines include, but are not limited to, the following: measles, mumps, rubella, varicella/zoster, yellow fever, rabies, BCG, and typhoid vaccine. Seasonal influenza vaccines for injection are generally killed virus vaccines and are allowed; however, intranasal influenza vaccines (eg, FluMist®) are live attenuated vaccines and are not allowed. Prior treatment with an anti-PD-1, anti-PD-L1, or anti-PD-L2 agent or with an agent directed to another stimulatory or co-inhibitory T-cell receptor (eg, CTLA-4, OX-40, CD137)
- Prior systemic anti-cancer therapy including investigational agents within 4 weeks prior to study start.

Note: Participants must have recovered from all AEs due to previous therapies to ≤Grade 1 or baseline. Participants with ≤Grade 2 neuropathy may be eligible.

Note: If participant received major surgery, they must have recovered adequately from the toxicity and/or complications from the intervention prior to starting study treatment.

- Prior radiotherapy within 2 weeks of start of study treatment to sites outside the breast. Participants must have recovered from all radiation-related toxicities, not require corticosteroids, and not have had radiation pneumonitis.
- Currently participating in or has participated in a study of an investigational agent or has used an investigational device within 4 weeks prior to the first dose of study treatment.

Note: Participants who have entered the follow-up phase of an investigational study may participate as long as it has been 4 weeks after the last dose of the previous investigational agent.

**4.2.11** For subjects who agree to the research breast MRI sub-study: Four or more previous gadolinium contrast scans due to the risk of brain deposits following repeated use of gadolinium-based contrast agents.

## 5.0 TREATMENT PLAN

### 5.1 Treatment Dosage and Administration

#### 5.1.1 Pembrolizumab

Subjects will receive pembrolizumab 200 mg as an IV infusion. Pembrolizumab will be administered as a 30-minute IV infusion (every effort should be made to target infusion timing to be as close to 30 minutes as possible. However, given the variability of infusion pumps from site to site, a window of -5 minutes and +10 minutes is permitted (i.e., infusion time is 30 minutes: -5 min/+10 min).

##### 5.1.1.1 Pembrolizumab Agent

Pembrolizumab is manufactured by Merck. Please refer to investigator brochure and MK-3475 Drug Preparation Instructions' manual.

**Table 1: Product Descriptions**

Product Name & Potency	Dosage Form
Pembrolizumab 50 mg	Lyophilized Powder for Injection
Pembrolizumab 100 mg/ 4mL	Solution for Injection

The investigator shall take responsibility for and shall take all steps to maintain appropriate records and ensure appropriate supply, storage, handling, distribution and usage of investigational produce in accordance with the protocol and any applicable laws and regulations. Clinical supplies will be affixed with a clinical label in accordance with regulatory requirements.

#### 5.1.2 RT Boost

The Gross Target Volume (GTV) for the boost will be defined by preoperative imaging +/- clips placed into the tumor at the time of the biopsy. A planning target volume (PTV) will be created from the GTV as per departmental partial breast irradiation treatment planning guidelines. The PTV will be treated with 8 Gy x 3 fractions (24 Gy total) with external beam techniques. RT will

begin within 5 calendar days of the second dose of pembrolizumab.

A total dose of 24 Gy will be delivered over 3 fractions within a 3 to 5-day period. Doses of 8 Gy will be given once daily for 3 treatment days.

**Figure 3**

A: Beams-eye view of the boost directed to the PTV. B: Axial and coronal views of the PTV with isodose lines denoting the radiation doses delivered with partial breast irradiation.

#### 5.1.2.1 Modality and Energy

Any combinations of photon beams of energy 6 MV or higher, with or without the addition of electrons of any energy, may be used for treatment, provided the dosimetric requirements of adequately treating the planning target volume (PTV) and homogeneity are met, although mixed energy (photons and electrons) is encouraged to minimize the exposure of the lung to radiation.

#### 5.1.2.2 Patient Positioning and Simulation

The patient will be simulated in the supine positioning in a breast board or alpha cradle.

#### 5.1.2.3 Target and Normal Structure Delineation

The radiation oncologist will identify the tumor by utilizing diagnostic MRI and mammographic imaging as the presence of clips in the breast. A radiopaque wire will be placed around the extent of the palpable breast tissue to delineate the whole breast volume. Axial non-contrast CT images will be obtained in 2.5 mm thick slices, superiorly from the angle of the mandible through the lung bases, except for the region of the tumor, where slice thickness will be narrowed to 1.25 mm to ensure precision in identifying the tumor. Following the initial scan, a review of the CT images will be performed to confirm the location of the primary tumor to be targeted. Tattoos will be placed in the same number and configuration as those for traditional whole breast treatments.

The radiation oncologist will outline the tumor, utilizing MRI or mammographic imaging to delineate the volume. A margin of 2 - 5 mm will be added superiorly, inferiorly, medially, and laterally to the tumor gross treatment volume (GTV) in order to create the PTV; the border of the PTV will be limited anteriorly to within 5 mm below the skin surface and posteriorly to the anterior chest wall, i.e. the anterior surface of the ribs. No attempt will be made to include the entire length of the incision scar.

The margins to be given around the excision volume will be determined in relation to the maximum diameter of the tumor GTV. If the maximum diameter of the tumor GTV is 4 cm or less, then up to 5 mm margins around it should be used. If the maximum diameter is larger than 4 cm, then 2 – 4 mm margins should be used. It is preferred the PTV does not exceed 30-35% of the

breast volume. Estimation of the PTV will be performed immediately after the simulation.

It is also required that 50% of the non-target breast tissue (ipsilateral breast volume minus the PTV) does not receive more than 50% of the prescribed dose. Additional margin beyond the PTV to the field edges will be added as required to achieve full dose (100%) to the PTV. Blocks or multileaf collimators should be used to define the treatment area.

#### **5.1.2.4 Dose-Volume Histogram and Normal Tissue Constraints**

The following structures should be contoured for all patients by the radiation oncologist:

1. Whole breast
2. Tumor CTV
3. Tumor PTV
4. Ipsilateral lung
5. Contralateral lung
6. Heart
7. Nipple

A dose-volume histogram (DVH) with volumes expressed as % total will be submitted and the dosimetry forms will be completed using the DVH data of the following:

1. Ipsilateral lung
2. Contralateral lung
3. Heart
4. Skin
5. PTV
6. Breast minus PTV

#### **5.1.2.5 Treatment Dose**

The dose delivered will be 8 Gy in 3 fractions (for a total of 24 Gy), given once daily over 3-5 days. Treatment may be started on any day of the week, but preferably on a Monday or Tuesday in order to allow for completion of RT prior to the weekend.

#### **5.1.2.6 Prescription Point**

The minimum isodose line that completely encompasses the PTV on the transverse, sagittal and coronal planes through the center of the PTV. Inhomogeneity corrections are to be used.

#### **5.1.2.7 Time-Dose Considerations**

- Dose per fraction: 24 Gy to the isodose line that completely encompasses the PTV
- Deliver one fraction per day to the isodose line that completely encompasses the PTV
- Total elapsed time: 3 to 5 days, unless there is a treatment break or interruption

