## STUDY SCHEMA

This is a prospective, phase Ib/II study of the preoperative combination of pembrolizumab (pembro) and radiation therapy (RT) in patients with operable breast cancer. Patients with newly diagnosed, Stage I-III breast cancer who are planned for breast-conserving surgery and adjuvant whole breast radiation therapy will be recruited into one of 2 cohorts as per their biomarker profile as depicted below. The TNBC cohort will have 50 subjects (10 TNBC subjects for phase Ib and 40 TNBC subjects for phase II) and the HR+ cohort will have 10 subjects. Enrollment will start with the phase Ib TNBC cohort. The trial will be conducted in a Bayesian design, wherein safety as assessed by lack of delay in standard of care treatment will be assessed after 3, 6, and 9 patients have initiated standard of care treatment in each cohort. Standard of care treatment is defined as breast-conserving surgery or initiation of neoadjuvant systemic chemotherapy. If the phase Ib TNBC trial meets a pre-specified safety endpoint, enrollment in

the phase II TNBC trial and HR+ cohort will take place.

Study treatment will consist of 2 doses of neoadjuvant pembro. The second dose will be given in combination with a RT boost. The primary objectives are: 1) to assess the feasibility of the preoperative combination of pembro and RT as defined by the number of patients who do not necessitate a delay in standard of care treatment, 2) to assess the change in tumor infiltrating lymphocyte (TIL) score with therapy. The secondary objectives are to describe the toxicity with preoperative pembro and RT up to 15 weeks after administration of pembrolizumab, to assess the invasive disease-free (iDFS) survival, and to assess the pathological complete response (pCR) rates.

- The first dose of pembro will be given on cycle 1, day 1 (C1D1). Each cycle will be 21 days. The second of pembro dose will be given on C2D1 (+/- 3 days).
- RT will be administered concurrently within one week of the second dose of pembro (C2D1 + 5 calendar days). 8Gy will be delivered in 3 fractions over 3 to 5 business days (for a total dose of 24Gy).
- Standard of care treatment, including breast-conserving surgery or additional neoadjuvant systemic therapy, will be pre-set to start 8 weeks after study enrollment (+/- 5 days).
- Research blood and stool will be obtained after consent up to C1D1. It will also be obtained on C2D1 (+/- 3 days) and at the time of initiation of standard of care treatment (+/- 5 days).

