### **1.4.3 Dose and Fractionation of RT with Immune Therapy**

Multiple studies have examined the role of radiation dose and fractionation in generating systemic anti-tumor immune responses. In murine models of RT, several groups have demonstrated enhanced production of circulating IFN-gamma expressing, tumor-specific CD8+ T cells with a single fraction of RT (15 Gy) delivered focally to tumors. Dewan et al reported that a hypofractionated dose of 8 Gy x 3 fractions was more effective than single fraction therapy when combined with anti-CTLA-4 therapy and resulted in increased TILs. Furthermore, in a 4T1 mammary carcinoma model, when CTLA-4 was combined with RT, two fractions of 12Gy each improved survival compared to single fraction. In a phase I dose-escalation trial of single-dose preoperative partial breast irradiation in early stage breast cancer patients, expression of genes immune-modulatory genes was increased in a dose-dependent fashion with single fraction RT.

Although there is no consensus regarding the optimal dose and fractionation of RT to utilize with immune therapies, it appears reasonable that higher total doses and that relative to single fraction, short, hypofractionated courses of fractionation generate greater antigen release, leading

to improved anti-tumor immune responses. In this study, we plan to use 8 Gy x 3 fractions on the basis of preclinical data from Dewan et al.

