#### **5.1.2.8 Homogeneity and Reference Points**

- The dose within the PTV must be within 100-125% of the prescribed dose
- The minimum isodose line that completely encloses the PTV on the transverse, sagittal and coronal planes through the center of the PTV.

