#### **5.5 Other Modalities or Procedures/ Research vs. Standard of Care Procedures**

A RT boost is a standard component of RT planning and usually follows WBRT after breast-conserving surgery. In this study, the boost will be administered preoperatively at a dose of 8 Gy for 3 fractions, to begin within 5 days of the second dose of pembrolizumab. RT will be performed using external beam ionizing radiation in accordance with institutional standard practice.

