## 6.4 Time and Events Table

	Screening ≤ 28 days 	Week 1 (C1D1)	Week 4 (C2D1)	Week 7 (SOC Tx)	Post Treatment Follow Up Q3W until week 19 & Q6 Mo. post Tx for 1 YR	Long-Term Follow Up Q6mos for up to 5 years post Tx
Pembrolizumab 		X	X			
Radiation Treatment 			X			
Initiation of Standard of Care Treatment 				X		
Eligibility Criteria	X					
Informed Consent	X					
Pathology Reviewed by Investigator	X					
Medical History	X					
EKG	X					
Height and weight	X					
History of present illness 	X	X	X	X	X	
Safety bloodwork 	X	X	X	X		
Full thyroid function panel (TSH, free and total T3 and free T4),		X 		X	X	X 
Cortisol						X 
ACTH, FSH/LH, prolactin, testosterone	X					
Amylase, lipase, LDH,	X					
PT/INR and aPTT	X					
HIV, Hepatitis B and C 	X					
Pregnancy test 	X	X				
Research bloods 	X		X	X		
Research tumor biopsy 	X		X	X	X	
Optional research breast MRI	X		X	X		
Optional fecal samples for microbiome analysis 	X		X	X		
Cosmesis Evaluation and Digital Photos 	X			X	X 	
Survival Status						X

1. Each cycle, 3 weeks (21 days) in duration, corresponds to 1 completed pembrolizumab treatment. Pembrolizumab will begin on C1D1. The second dose will be given on C2D1 (+/- 3 days).
2. RT will consist of 8Gy for 3 fractions. RT will be delivered concurrently with the second dose of pembrolizumab within 5 business days of C2D1
3. Initiation of standard of care treatment consisting of either breast-conserving surgery or neoadjuvant systemic therapy will begin 3 weeks after the second dose of pembrolizumab (+/- 5 days).

4. Procedures must be performed within 28 calendar days prior to C1D1.
5. A history of present illness (HPI) consisting of physical examination, vital signs (including temperature, pulse rate, respiratory rate, blood pressure), performance status assessment, medication reconciliation, and toxicity/adverse event assessment will occur at each visit, prior to study treatment administration if due. AE collection will continue until week 19, immune related AE collection (listed in table 2) will continue until 1 year post treatment

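### Section 5.1.2.7 gives the 24 Gy total boost dose as the dose per fraction; the rest of the protocol supports 8 Gy per fraction

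*Combined protocol and SAP*

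**What the plan says.** Section 5.1.2.7 sets the time-dose instructions for the preoperative boost. Its dose bullet reads "Dose per fraction: 24 Gy to the isodose line that completely encompasses the PTV". The other two bullets call for one fraction a day and an elapsed time of 3 to 5 days. The section gives neither the number of fractions nor a total dose.

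The boost is described in eight other places:

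- Section 5.1.2 gives 8 Gy by 3 fractions, 24 Gy in total, and adds: "Doses of 8 Gy will be given once daily for 3 treatment days".
- Section 5.1.2.5: "The dose delivered will be 8 Gy in 3 fractions (for a total of 24 Gy), given once daily over 3-5 days".
- Study Schema: "8Gy will be delivered in 3 fractions over 3 to 5 business days (for a total dose of 24Gy".
- Section 1.4.3: "we plan to use 8 Gy x 3 fractions on the basis of preclinical data".
- Section 5.5: "the boost will be administered preoperatively at a dose of 8 Gy for 3 fractions".
- Section 6.4, footnote 2: "RT will consist of 8Gy for 3 fractions".
- The Study Summary and the Study Intervention part of Section 3.0 also give 8 Gy and 3 fractions.

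**The concern.** The bullet in 5.1.2.7 and the schedule in 5.1.2 cannot both be followed. One calls for 24 Gy at each daily treatment, the other for 8 Gy. Section 10.7 requires the study to be run as the approved protocol describes, apart from emergencies and approved exceptions. Giving the correct 8 Gy therefore departs from 5.1.2.7, and giving 24 Gy departs from 5.1.2 and 5.1.2.5.

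The stakes concern treatment and safety. This is the dose of an experimental component, in the radiation planning section, for patients treated with curative intent. Some of the plan's own checks would not catch a wrong entry because they scale with the prescription. Section 5.1.2.8 is one: "The dose within the PTV must be within 100-125% of the prescribed dose". The heart and liver maxima, each set at 90% of the prescription, and the half-dose limit on non-target breast in 5.1.2.3 behave the same way.

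**Working it through.** **Inputs.** The statements of the boost, side by side:

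| Place | Dose per fraction | Fractions | Total |
|---|---|---|---|
| Study Schema | 8 Gy, implied by the total | 3 | 24 Gy |
| Study Summary | 8 Gy | 3 | not stated |
| 1.4.3 | 8 Gy | 3 | not stated |
| 3.0, Study Intervention | 8 Gy | 3 | not stated |
| 5.1.2 | 8 Gy | 3 | 24 Gy |
| 5.1.2.5 | 8 Gy, implied by the total | 3 | 24 Gy |
| 5.5 | 8 Gy | 3 | not stated |
| 6.4, footnote 2 | 8 Gy | 3 | not stated |
| **5.1.2.7** | **24 Gy** | not stated (one a day) | not stated |

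**Step 1: reproduce the stated total.** Total dose = dose per fraction × number of fractions. From 5.1.2: 8 × 3 = 24 Gy, which matches.

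**Step 2: put the 5.1.2.7 figure into the same formula.** 24 × 3 = 72 Gy, which does not match. The ratio is 72 / 24 = 3, the same as 24 / 8 = 3 per fraction.

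**Step 3: look for a reading that rescues the line.**

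- If 24 Gy is meant as the total, it contradicts the bullet's own label.
- If 24 Gy is meant as a single treatment, 24 × 1 = 24 Gy gives the right total. It contradicts the three once-daily fractions in 5.1.2 and 5.1.2.5, and it does not fit the 3 to 5 days in 5.1.2.7 itself.

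**Step 4: check the two loosely worded places.** The Study Schema and 5.1.2.5 attach 8 Gy to the set of three fractions. Taken alone, that could mean 8 / 3 = 2.67 Gy per fraction. Both add that the total is 24 Gy, and 24 / 3 = 8 Gy per fraction, so they support 5.1.2.

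**Step 5: rule out other doses.** The 16 Gy boost in 1.4.1 belongs to a cited trial. The 200 cGy × 25 course under Standard of Care Therapy is the postoperative whole-breast treatment. Neither describes the study boost.

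**Step 6: see how the prescription-based limits move.**

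| Limit | At 24 Gy total | At 72 Gy total |
|---|---|---|
| PTV, 100–125% | 24 to 1.25 × 24 = 30 Gy | 72 to 1.25 × 72 = 90 Gy |
| Heart and liver maximum, 90% | 0.90 × 24 = 21.6 Gy | 0.90 × 72 = 64.8 Gy |

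These limits would pass a plan built on the wrong figure. The limits in absolute dose do not move: in skin, a 12 Gy point maximum and at most 1 cc above 10 Gy; in lung, at most 3% of the volume at 20 Gy; in liver, no more than 5 Gy to 20% of the organ.

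**The case against.** The strongest reply is that this is a clerical slip with one obvious correction. The right schedule stands in 5.1.2, which opens the boost instructions, and 5.1.2.5 comes only two headings before the faulty line. Section 5.1.2.7 gives no fraction count, so reaching 72 Gy means borrowing the count of 3 from sentences that mostly sit beside the correct dose or total. Several absolute limits on skin, lung and liver could expose a tripled dose. No endpoint, decision rule or error rate changes. The inconsistency is also less one-sided in precision than a count of eight against one suggests: only the Study Summary, 1.4.3 and 5.1.2 are fully unambiguous, and Sections 3.0, 5.5 and 6.4 use slightly loose wording without a total.

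Most of this stands. Misdelivery is unlikely, and the problem is better described as an internal inconsistency than as a failed calculation. Whether each absolute limit would flag a bad plan depends on tumour position, which the documents do not give, so those limits cannot be counted on in every case. None of this makes 24 Gy per fraction correct. It bears on the chance of harm, not on whether the instruction is wrong.

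**Conclusion.** The concern holds. The bullet in 5.1.2.7 is current protocol text and is wrong as written: it prints 24 Gy where 8 Gy is intended, a threefold error. With the three fractions stated elsewhere it would imply 72 Gy in place of 24 Gy. The intended dose is not in doubt. That the total was put on the per-fraction line is an inference, though no other explanation fits as well. The conclusion rests only on the protocol's own dose statements and needs no outside figure. There is no effect on sample size, power or type I error. It must be corrected because it is an operative dose instruction for the experimental treatment.

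**What to change.** In Section 5.1.2.7, change the dose bullet to 8 Gy per fraction, add in brackets that the total is 24 Gy in 3 fractions, and leave the rest of the line unchanged. In the Study Schema and Section 5.1.2.5, reword the dose as 8 Gy per fraction × 3 fractions, so that the meaning no longer depends on the total that follows.

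The cost is a text correction in one amendment, with no effect on patients, sample size or timelines.

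Two separate editorial checks could go into the same amendment; the conclusion does not rest on them. First, the lung constraint at 20 Gy appears three times for each lung in 5.1.2.9 and should be checked against the source PDF and the source constraints. Second, the window for starting radiation is 5 calendar days in the Study Schema and 5.1.2 but 5 business days in 6.4, footnote 2, and should be aligned.
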